## Introduction:

The need for improving newborn and infant health and the behaviors that contribute to outcomes in Ethiopia is clear. One in every 17 Ethiopian children die before their fifth birthday and 7 in 10 of those deaths occur during infancy. Causes for newborn mortality are not always well documented, but literature suggests that prematurity, asphyxia, and infection are leading causes of newborn and infant death. Infections in newborns remain a large threat to newborn survival in Ethiopia. Acute infections causing pneumonia, fever, and diarrheal disease contribute substantially to the burden (over 31%) of under five deaths, and less than half of children with reported symptoms sought any care or treatment according to recent estimates.

While both child and infant mortality rates have dropped substantially over the past 15 years, progress in reducing newborn deaths has been slower pointing to challenges and complexities in changing behaviors and practices around identifying illness and delivering newborn care. For children who do survive, poor nutrition and its impacts on growth and development are widely observed. Seven percent of children in Ethiopia suffer from acute malnutrition (wasting). Perhaps more importantly, in Ethiopia, 37% of children under five in Ethiopia are stunted, or below their expected height for age, a sign of chronic undernutrition. Stunting is associated with significantly higher rates of mortality, with cognitive and developmental delays and with lower income earning potential. Ultimately, stunting is a critical driver of poor economic development in many low-income settings. This clearly represents an important intervention opportunity to improve survival, development, and productivity.

Optimizing nutrition in young infants is one of the most effective interventions to improve infant survival and growth. In Ethiopia, only 14% of children age 6-23 months meet the minimum acceptable dietary standards and, in the Amhara region where SCOPE works, only 7% of children under two years old get the minimum dietary diversity they need for healthy growth and development. Exclusive breastfeeding in the first six months of life has the potential to dramatically improve growth and survival. However, cultural and social pressures often result in cessation of exclusive breastfeeding at younger ages, with significant impacts on future growth and development.

Healthcare providers have limited interactions with women when they leave a health facility after birth. While home visitation is nominally a pillar of postnatal care, logistical challenges to follow-up and systematic implementation of home visits remains challenging in Ethiopia, where only 34% of women with registered births receive any postnatal care. In addition, only half (48%) give birth in a health facility and

---

 Mengesha, H. G., & Sahle, B. W. (2017). Cause of neonatal deaths in Northern Ethiopia: a prospective cohort study. *BMC Public Health*, 17, 62. <http://doi.org/10.1186/s12889-016-3979-8>

 BerheWeldearegawi et al. *BMC Public Health* 2015;15:770 <https://doi.org/10.1186/s12889-015-2090-x> 11 August 2015.

 Central Statistical Agency - CSA/Ethiopia and ICF. 2019. Ethiopia Demographic and Health Survey 2019. Addis Ababa, Ethiopia: CSA and ICF. Available at <https://dhsprogram.com/pubs/pdf/FR363/FR363.pdf>

 Central Statistical Agency - CSA/Ethiopia and ICF. 2019. Ethiopia Demographic and Health Survey 2019. Addis Ababa, Ethiopia: CSA and ICF. Available at <https://dhsprogram.com/pubs/pdf/FR363/FR363.pdf>.

 Central Statistical Agency - CSA/Ethiopia and ICF. 2019. Ethiopia Demographic and Health Survey 2019. Addis Ababa, Ethiopia: CSA and ICF. Available at <https://dhsprogram.com/pubs/pdf/FR363/FR363.pdf>

would be registered for such visits. Several critical elements of essential newborn care and early infant feeding can be practiced at home and in the community including exclusive breastfeeding, kangaroo mother care, feeding, hygiene, and early identification of infections. Partnerships with faith leaders may provide a culturally relevant platform for accessing women and infants, increasing uptake of practices known to improve infant health and development, and providing support for women in the postnatal period and throughout the first year of their child's life.

## Study Objectives:

The **primary objective** of the study is to determine the impact of a behavior change intervention that partners Orthodox priests with members of the Health Development Army (HDA) and trains them to conduct newborn health outreach to increase rates of early initiation of and exclusive breastfeeding through 6 months and vaccination coverage at 6 months.

Secondary objectives include:

- Determine the impact of the intervention on infant growth at six months, observed and self-reported changes in nutrition and feeding practices of mother and infants, and early identification of newborn illness.
- Design a culturally relevant, scalable intervention for community-based newborn and infant health in Gondar in partnership with local partners, the Federal Ministry of Health, and the Gondar Regional Health Bureau.

## Methods:

### Study Design:

In collaboration with the woreda administrative office and the woreda diocese of the EOC, all the kebeles and EOC churches in the woreda will be mapped by the study team and randomly assigned to intervention or control. Sites will be selected in a way that ensures they are reasonably far apart in order to avoid contamination. Newborn-mother pairs in the catchment areas of the intervention churches will receive the intervention, whereas those in the control churches will receive routine community health packages implemented by community health workers (HEWs and HDAs).

The intervention will be implemented at the community level by pairs of trained EOC priests and members of the HDA. A list of priests serving at the EOC churches in the intervention arm will be obtained through the woreda diocese and their respective churches. All the priests will be contacted through the church leadership and asked to participate in the study intervention. The intervention will be implemented in collaboration with HDA members recruited by HEWs under the health centers in the catchment areas of the intervention churches. HDA members 55 years old or younger will be asked to participate.

An initial 5-day training will be given to priests and HDA members. The training will focus on newborn health topics including early initiation of and exclusive breastfeeding, maternal nutrition, immunization, childhood illnesses, child health care services, etc. At the end of the training action plans will be prepared by the training organizers, priests, and HDA. Priest will be asked to integrate health messages

---

 Central Statistical Agency - CSA/Ethiopia and ICF. 2017. Ethiopia Demographic and Health Survey 2016. Addis Ababa, Ethiopia: CSA and ICF. Available at <http://dhsprogram.com/pubs/pdf/FR328/FR328.pdf>.

and education into their routine family visits around the birth of a child in structured intervals as culturally appropriate.

The trained priests and HDA members will be dispatched to their respective communities to begin the intervention. Their primary activities will be identification of near-term pregnant and newly delivered women, providing health education to their families, follow-up visits to enable newborn-mother pairs to access child health care services, and to provide health education at religious and community gatherings. Specifically, pre-planned visits of parishioners' families will be done by the respective priests and the partnering HDA members during the last month of pregnancy, immediately after the delivery of the baby and around the time of baptism for the newborn. These visits will be used to educate pregnant and postpartum women and their families on newborn health topics including initiation of breastfeeding, duration of breastfeeding/ exclusive breastfeeding, vaccination, cord care, and utilization of available newborn health care services. These community-based activities will be monitored through regular follow-up visits by the UoG study team and discussions with priests and HDA members.

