**Methods:** The study utilizes a community-randomized trial design in which 11 communities will be randomized to receive the intervention and 11 communities will be randomized as control communities. The unit of randomization at the house of worship. The target population for this undertaking is pregnant women and women who recently delivered in rural communities in the North Gondar region of Ethiopia. Infants enrolled in the study will have a baseline evaluation within 10 days of birth and the primary outcomes of mid-upper arm circumference (MUAC) and exclusive breastfeeding will be measured at a follow-up visit at between 5 and 6 months after birth. The sample size of 150 infants from intervention churches and 150 infants from control churches is based on identifying a statistically significant difference of  $\geq 0.2$  cm in mid-upper arm circumference (MUAC) with 80% power at  $\alpha=0.05$ , anticipating 20% of participants being lost to follow-up. We will also have 80% power to detect a significant difference of 50% exclusive breastfeeding at 5-months in the control group versus 70% in the intervention group.

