## **Statistical analysis plan**

We will compare infant outcomes between children exposed to the intervention and those in control communities. We will use logistic regression to compare dichotomous outcomes (e.g., exclusive breastfeeding through 6 months, completion of vaccinations, infant hospitalization) and linear regression for continuous outcomes (e.g., mid-upper arm circumference). Primary outcomes will be evaluated using an intention-to-treat analysis without adjustment for other covariates. We will account for correlation within church communities by adjusting the variance for the effect of clustering.

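### With only 22 churches, the plan describes no balancing of the arms at allocation and no covariate adjustment of the primary outcomes; stratifying on a mapped site feature would be a cheap gain in precision and credibility

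*Combined protocol and SAP*

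**What the plan says.** The Summary sets the size of the randomisation: "11 communities will be randomized to receive the intervention and 11 communities will be randomized as control communities". It names the unit as the church: "The unit of randomization at the house of worship". The Study Design section describes the procedure in one sentence: "all the kebeles and EOC churches in the woreda will be mapped by the study team and randomly assigned to intervention or control". No way of generating the sequence is named, and no strata, matching or balance criterion appears anywhere in the document.

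The one restriction on sites concerns spacing: "Sites will be selected in a way that ensures they are reasonably far apart in order to avoid contamination". It guards against contamination and does nothing to make the arms alike.

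The Statistical analysis plan then states: "Primary outcomes will be evaluated using an intention-to-treat analysis without adjustment for other covariates". The same section corrects the variance for correlation within church communities but does not name the method. The Data Collection section lists several predictors other than the intervention. They are mainly maternal and family characteristics, none of those named is a feature of the site, and the unadjusted primary analysis does not use them.

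**The concern.** Parishes may differ in ways that matter for feeding, vaccination and care-seeking, for instance in distance from the health centre. With hundreds of randomised units such differences even out. With 22 they often do not. A plan can deal with this when it allocates, by stratifying or constraining, or when it analyses, by adjusting for a prespecified site factor. This plan describes neither, although the team will map the churches before assigning them.

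Two things are at stake. The between-church spread stays in the error term of the primary comparisons and lowers power. And if the arms turn out visibly unequal on an obvious site feature, the single trial result is harder to believe, whichever way it falls.

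**Working it through.** **The plan's own figures.** The Summary gives 150 infants per arm, "anticipating 20% of participants being lost to follow-up", so 150 × (1 − 0.20) = 120 per arm complete. This agrees with the 240 pairs under Number of Subjects, and is 120/11 = 10.9 per church.
- MUAC: no SD is given, so the calculation cannot be reproduced independently. Solving 0.2 = (1.96 + 0.842) × SD × √(2/120) gives SD = 0.553 cm with no design effect (two-sided test assumed).
- Exclusive breastfeeding, 50% versus 70%: 93 per arm gives 80% power. With 120 per arm and no clustering, power is 89% with the pooled-variance formula and 90% with the unpooled one.

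**Chance splits.** The documents give no site effect, ICC or between-site SD, so assume a feature held by 11 of the 22 churches. Under unrestricted 11:11 allocation the number in one arm is hypergeometric (22, 11, 11):
- 6-5: 2 × 462²/705,432 = 0.605
- 7-4: 2 × 330²/705,432 = 0.309
- 8-3 or worse: 1 − 0.605 − 0.309 = 0.086

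So 7-4 or worse has probability 0.395 (39.49% unrounded).

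**Shift in the arm difference.** Shift = (difference between arms in the share of churches with the feature) × (effect of the feature). The share differs by 3/11 at 7-4 and by 5/11 at 8-3.

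| Assumed effect of feature | 7-4 split | 8-3 split | Share of 20-point target |
|---|---|---|---|
| 10 points | 2.7 points | 4.5 points | 14% and 23% |
| 20 points | 5.5 points | 9.1 points | 27% and 45% |

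For scale, two equal-sized groups of churches 10 points apart correspond to an ICC of about 0.05²/(0.6 × 0.4) = 0.010. Groups 20 points apart correspond to about 0.10²/(0.6 × 0.4) = 0.042.

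**Power for exclusive breastfeeding.**
- Sampling SE = √[(0.50 × 0.50 + 0.70 × 0.30)/120] = 0.0619.
- The SD of the difference in shares over allocations is (2/11) × √(11 × ½ × ½ × 11/21) = 0.218. This gives 0.0218 for a 10-point feature and 0.0436 for a 20-point feature.
- Total SE = √(0.0619² + 0.0218²) = 0.0656, or √(0.0619² + 0.0436²) = 0.0758.
- Power = Φ(0.20/SE − 1.96) = 90% with no site effect, 86% at 10 points and 75% at 20 points.

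The binomial SE already contains a little of the between-site variance. Removing that overlap gives 86% and 76%. These are normal approximations and so slightly generous with 20 between-church degrees of freedom.

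**MUAC, by ICC.** The typical (1 SD) between-site shift is √ICC × 0.553 × √(2/11). As a share of 0.2 cm it is 12% at ICC 0.01, 26% at 0.05 and 46% at 0.15. The ICCs are assumptions, and the SD is the back-solved one. If the 120 already contained a design effect, the SD would be smaller and the last two shares would be 22% and 29%.

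**What restriction recovers.** If the strata explain half the between-site variance (assumption), the typical MUAC shift falls from 26% to 19% of target at ICC 0.05, and from 46% to 32% at ICC 0.15.

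**The case against.** The strongest reply is that the planned analysis is valid as it stands. Random assignment of churches is unbiased over allocations. If the cluster adjustment is done properly for 22 clusters, chance differences between churches are already in the standard error and type I error is held. This stands. A reader might infer that an unlucky split would bias the trial; the documents do not support that. The adjustment widens the interval to cover the imbalance, but it does not recover the lost precision.

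A reader might also infer that the plan uses simple randomisation. It does not say so. The arms are fixed at 11:11, which independent coin tosses would produce only 17% of the time, and the method is just not reported. A restricted scheme may exist that the document leaves out.

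Third, the sizes are conditional. The best possible 6-5 split arises in about 61% of allocations. Working in one woreda and enrolling only Orthodox parishioners may narrow the differences between sites. Nor is the drop from 90% to 75% or 86% the gain from stratifying: it compares no site effect with a site effect, and stratification returns only what the strata explain. All of this stands, and it limits the point to an improvement in efficiency.

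Last, the plan says that churches are mapped, not that parish characteristics are recorded. That is fair, and the fix has to provide for it.

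**Conclusion.** The point holds as a worthwhile, low-cost improvement. The document describes no balancing of 22 churches at allocation and no adjustment of the primary outcomes in the analysis. For a feature held by half the churches, a 7-4 split or worse has probability 39%, and 8-3 or worse 8.6%. Those splits move the exclusive breastfeeding difference by 14% and 23% of the target if the feature is worth 10 points, or by 27% and 45% if it is worth 20. Power is about 86% or 75%, against about 90% with no site effect; the 20-point case falls below the 80% that the Summary claims.

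The prevalence of the feature, its effect and the ICCs are all assumptions. It is tempting to conclude that imbalance will move the result by a quarter to nearly half of the target. That follows only if one site feature is worth the full 20 points, and nothing in the documents establishes this. The supportable conclusion is lost precision and a less credible single result, in a trial that remains valid without the change.

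**What to change.** **Study Design.** State how the allocation is generated. Once the 22 churches have been selected, form two to four strata from a feature that can be read from the map, for example distance to the health centre. Set the cut-points so that each stratum holds an even number of churches, and allocate 1:1 within strata. Two strata of 11 would not do: each would have to split 6-5, leaving a residual shift of 1/11 (9%) of the feature's effect.

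**Statistical analysis plan.** Include the randomisation stratum in the primary models, keep the cluster-adjusted variance, and amend the sentence on covariates to match. In the logistic models the odds ratio then becomes conditional on stratum, and the plan should say so.

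**If allocation is already done.** Report the method used, and prespecify one or two site-level covariates before outcome data are seen.

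**Cost.** Wording in two sections, one to three fewer between-church degrees of freedom out of 20, and the need to record the stratifying feature during mapping. No more participants or study visits are needed.

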### **Prospective follow-up**

Research assistants will work for the zonal health office to identify all births occurring in the study area. Independent of the intervention outreach teams, the research assistants will attempt to contact all newborn-mother pairs within 10-days of birth. Most contacts will occur at home, but contact may be made at other locations (e.g., health facility, church). Mothers will be invited to participate in the study, and each participating newborn-mother pair will be followed-up by the study team for up to 6 months after enrollment.

### **Data Collection**

The UoG study team will conduct regular visits in both the intervention and control communities to screen, consent, and register new newborn-mother pairs reported by HEWs, collect baseline data from them, arrange follow-up visit schedules, and collect follow-up data from previously enrolled study participants. Each newborn-mother pair will receive up to three visits by the study team in the sixth month period. The study team will use OpenDataKit (ODK), an electronic data collection system to record data on tablets. The study team will upload the collected data to a secured central web-based server upon return to the UoG campus. The overall processes of recruitment and subsequent data collection activities will be supervised by an on-site study manager. The study team will rely heavily on pre-designed standard operating procedures that contain detailed, step-by-step instructions for collecting and handling data.

The following primary and secondary outcome variables will be assessed in this study:

**Primary outcome variables:** mid-upper arm circumference (MUAC), proportion of mothers exclusive breastfeeding

**Secondary outcome variables:** immunization status (complete vaccination and individual vaccines), frequency of acute illnesses, and frequency of hospitalization

**Predictors (other than intervention):** maternal age, sex of child, maternal education, family economic status, family size, etc.

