## Summary:

**Background:** One in every 15 Ethiopian children die before their fifth birthday and 7 in 10 of those deaths occur during infancy. Optimizing nutrition in young infants is one of the most effective interventions to improve infant survival and growth. In Ethiopia, only 7% of children age 6-23 months meet the minimum acceptable dietary standards and, in the Amhara region where this intervention will take place, only 3% of children under two years old get the minimum dietary diversity they need for healthy growth and development. The Amhara region is characterized by its religious tradition with 84% of the population belonging to the Ethiopian Orthodox faith tradition. Partnerships with faith leaders may provide a culturally relevant platform for accessing women and infants, increasing uptake of practices known to improve infant health and development, and providing support for women in the postnatal period and throughout the first year of their child's life.

**Objective:** The study aims to determine the impact of a behavior change intervention that partners Orthodox priests with members of the Health Development Army (HDA) and trains them to conduct newborn health outreach to increase rates of early initiation of exclusive breastfeeding through 6 months and vaccination coverage at six months. We will also determine the impact of the intervention on infant growth at between 5 and 6 months of age, observed and self-reported changes in nutrition and feeding practices of mother and infants, and early identification of newborn illness.

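### The primary objective and the two primary outcomes share only exclusive breastfeeding, and no success rule is given: if either outcome may count, the chance of a false claim of benefit is up to about 4.9% instead of 2.5%

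*Combined protocol and SAP*

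**What the plan says.** **Primary outcomes.** Data Collection gives "mid-upper arm circumference (MUAC), proportion of mothers exclusive breastfeeding". The Summary (Methods) agrees: "the primary outcomes of mid-upper arm circumference (MUAC) and exclusive breastfeeding will be measured at a follow-up visit". Neither is ranked above the other.

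**Primary objective.** Study Objectives describes outreach meant to "increase rates of early initiation of and exclusive breastfeeding through 6 months and vaccination coverage at 6 months". The Summary (Objective) names the same three items.

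**Secondary objectives.** Study Objectives includes "Determine the impact of the intervention on infant growth at six months", followed by "observed and self-reported changes in nutrition and feeding practices of mother and infants, and early identification of newborn illness". The Summary likewise puts growth after the main aim: "We will also determine the impact of the intervention on infant growth at between 5 and 6 months of age".

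**Secondary outcomes.** Data Collection lists "immunization status (complete vaccination and individual vaccines), frequency of acute illnesses, and frequency of hospitalization".

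**Timing.** The Summary says both primary outcomes "will be measured at a follow-up visit at between 5 and 6 months after birth". Its power statement puts exclusive breastfeeding at five months. The objectives and the Statistical analysis plan section carry it through six months.

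**Power and analysis.** The Summary bases 150 infants per arm on a MUAC difference of 0.2 cm, with 80% power, alpha 0.05 and 20% loss. It then claims 80% power for breastfeeding at 50% against 70%, without restating alpha. The Statistical analysis plan section specifies logistic and linear regression, intention-to-treat, no covariate adjustment for the primary outcomes, and a variance adjusted for clustering. It does not mention multiplicity or a criterion for success.

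**The concern.** The plan does not define a positive trial. With two primary tests and no rule, a reader could require both to succeed or, once the results are known, accept whichever one did. These readings have different error rates and different power, and the plan's alpha of 0.05 and power of 80% describe neither of them.

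The mismatch between objective and outcomes makes this worse. A trial significant on MUAC alone would have met a primary outcome without addressing any item named in its primary objective. A trial that raised vaccination alone would have met part of its primary objective through a secondary outcome. The one shared item, exclusive breastfeeding, is described over different periods.

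**Working it through.** **1. Objective against outcomes**

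| Item | In the objectives | In the outcome list |
|---|---|---|
| Exclusive breastfeeding | Primary | Primary |
| Early initiation | Primary | Not listed |
| Vaccination | Primary | Secondary |
| MUAC | Not named; fits best under growth, which is secondary (our reading) | Primary, and the basis of the sample size |
| Feeding practices; early identification of illness | Secondary | Not listed as such |

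**2. The plan's own figures**

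- Completers: 150 × 0.8 = 120 per arm, 240 in all. This matches the Number of Subjects table.
- MUAC: the sample size cannot be reproduced because no SD is given. The SD that yields 80% power with 120 per arm and no clustering is 0.2 / [(1.960 + 0.842) × √(2/120)] = 0.553 cm.
- Breastfeeding, 50% v 70%, 120 per arm, no clustering: z = (0.2 − 1.960 × √(2 × 0.6 × 0.4/120)) / √((0.25 + 0.21)/120) = 1.23, so power is 89.0%. Only 93 per arm are needed for 80%.
- The stated 80% for breastfeeding therefore fits a design effect of 120/93 = 1.29. With 240/22 = 10.9 completers per church, that is an ICC of (1.29 − 1)/(10.9 − 1) ≈ 0.03. The stated power may already allow for clustering, so the main results below add no design effect.

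**3. Error if either outcome counts**

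The correlation between the test statistics is not given, so a range is shown (bivariate normal).

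| Each test at | Error | Independent | r = 0.3 | r = 0.5 | One test |
|---|---|---|---|---|---|
| Two-sided 0.05 | Any false positive | 1 − 0.95² = 9.75% | 9.5% | 9.1% | 5% |
| Two-sided 0.05 | False benefit | 1 − 0.975² = 4.9% | 4.8% | 4.5% | 2.5% |
| One-sided 0.05 | False benefit | 1 − 0.95² = 9.75% | 9.3% | 8.8% | 5% |

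Whatever the correlation, the two-sided family-wise error cannot exceed 0.05 + 0.05 = 10%. At r = 0.7 it is 8.35%, with false benefit 4.17%. If both outcomes must succeed, error is at most 5%.

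Under Holm, with no true effect on either outcome and independent tests, the two-sided error is 1 − 0.975² = 4.9% and false benefit is 1 − 0.9875² = 2.5%.

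**4. Power, starting from the stated 80% for each outcome**

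A test with 80% power at 0.05 has 71.2% at 0.025.

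| Rule | Independent | r = 0.5 |
|---|---|---|
| Both must succeed | 0.8² = 64% | 69% |
| At least one, unadjusted | 1 − 0.2² = 96% | 91% |
| Holm, at least one | 1 − (1 − 0.712)² = 92% | 85% |
| Holm, each outcome | 0.712 + (0.800 − 0.712) × 0.712 = 77.5% | 76.5% |
| Fixed sequence, breastfeeding first: breastfeeding | 80% | 80% |
| Fixed sequence, breastfeeding first: MUAC | 64% | 69% |

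**5. If the stated MUAC power ignores clustering**

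Assume an ICC of 0.05 and independent tests. The design effect is 1 + 9.91 × 0.05 = 1.495, leaving 120/1.495 = 80.2 effective infants per arm. MUAC starts from the stated 80%, and breastfeeding from the calculated 89%.

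- MUAC: 63.0% unadjusted, 59.0% under Holm (4.0 points).
- Breastfeeding: 73.9% unadjusted, 69.0% under Holm (4.9 points).
- Both succeed: 0.630 × 0.739 = 47%.

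**The case against.** - **The inflation is conditional.** The plan nowhere says that either result would be claimed as success, and two distinct outcomes can be reported on their own terms. This is right as far as it goes: the firm defect is the missing rule, and 9.75% is what one permitted reading would cost. But the only reading that needs no adjustment is that both must succeed, and then the power for success is not 80%.
- **Correlation reduces it.** MUAC and breastfeeding come from the same infants. At correlation 0.5 false benefit is still 4.5% against 2.5%. At high correlation the excess is clearly smaller.
- **The objective may describe what the outreach aims for and not list endpoints.** The grammar allows this, and placing MUAC under growth is a reading. On any reading, MUAC is absent from the primary objective, and two items named there are not primary outcomes.
- **The time point is nearly settled.** Five months falls within the planned visit window. What remains is the six-month label, which a visit before six months cannot observe. This part is minor.
- **The secondary items are partly covered.** The questionnaire collects nutritional and illness history, and the frequency of acute illness is a listed outcome. That supplies data, but no listed outcome for feeding practices or early identification. This too is peripheral.
- **The 80%/80% starting point is uncertain.** If the stated power ignores clustering, breastfeeding has 89%, and the chance that both succeed is 0.80 × 0.89 = 71% before any design effect, or 47% at ICC 0.05. This stands, and the plan should say what its 80% includes.

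**Conclusion.** The concern holds and should be fixed. The objective and the primary outcomes agree on one item only, and nothing in the document says what makes the trial positive.

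If either outcome may count, the risk of a false claim nearly doubles at low to moderate correlation. The headline figures assume two tests at two-sided 0.05 each. Sidedness is not stated, and alpha is only implied for breastfeeding; 9.75% and 4.9% also assume independence. The power figures rest on the plan's stated 80% for each outcome. The textual finding and the error rates are secure; the power figures are less so, because the plan gives neither an SD nor an ICC.

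**What to change.** Before outcome data are seen:

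1. **Align objective and outcomes.** The least disruptive way is to reword the primary objective, in the Summary and in Study Objectives, to name MUAC and exclusive breastfeeding, because the sample size rests on MUAC. List vaccination and early initiation as secondary in both places. If the sponsor changes the outcomes instead, the sample size must be justified again. Give feeding practices and early identification of illness a listed outcome, or remove them from the objectives.
2. **Use one time point for exclusive breastfeeding throughout**, for example status as reported at the visit between 5 and 6 months.
3. **Add one success rule to the Statistical analysis plan section.** As the plan ranks neither outcome, suggested text is:

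> MUAC and exclusive breastfeeding are tested by the Holm procedure at a two-sided family-wise alpha of 0.05: the smaller p-value against 0.025 and, if significant, the larger against 0.05. The trial is positive if at least one is significant in favour of the intervention.

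   A fixed sequence, if the sponsor ranks one outcome first, or a both-must-succeed rule is also acceptable if stated.

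4. **State power under the chosen rule**, and say whether it allows for clustering.

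**Cost.** This is wording only, with no change in sample size if the outcomes stay and the lower power is accepted. From the stated 80%/80%, Holm costs about 2.5 points per outcome (3.5 at correlation 0.5). Power for at least one falls from 96% to 92% (91% to 85%) compared with an unadjusted either-outcome rule. In the ICC 0.05 case the cost is about 4 to 5 points per outcome. Restoring 80% per outcome under Holm with independent tests needs about 127 completers, or 127/0.8 ≈ 159 enrolled, per arm, with no further allowance for larger clusters. A fixed sequence costs the first outcome nothing and the second 16 points (11 at correlation 0.5). A both-must-succeed rule leaves 64% power (69%).
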